The duration of run-in period will be between a minimum of 14 and a maximum of 28 days (from Visit 2 to Visit 3). During the run-in period, all patients will receive ipratropium 20 µg × 2 puffs 4 times per day (must be discontinued 8 hours prior to previous any pulmonary function test). A paper diary will be used to collect AEs and concomitant medication during run-in and wash-out periods.

Treatment periods: After the screening period, patients must fulfil all inclusion and none of the exclusion criteria prior to being randomised at Visit 3. Eligibility results will be used from the Screening period for any assessments that cannot be completed within Visit 3 (eg, laboratory assessments).

The duration of each treatment period will be 14 days. In each treatment period, patients will receive 1 of the following 3 treatments according to a William's design with 3 periods and 6 sequences, using a balanced randomisation ratio per treatment sequence:

- AZD8871 600 µg once daily (double-blind).
- Anoro[®] Ellipta[®] (55 µg UMEC/ 22 µg VI) once daily (double-blind).
- Placebo (double-blind).

Each of the 3 treatment periods will include 2 overnight stays at the study site and 1 ambulatory visit at the study site.

Visits 3, 6 and 9 (corresponding to Treatment Day 1 in each period) and Visits 5, 8 and 11 (corresponding to Treatment Day 14 in each period) will include an overnight stay in the unit. At these visits, safety and tolerability assessments and pulmonary function measurements will be taken pre-dose and up to 24 hours post-dose.

Visits 4, 7 and 10 (corresponding to Treatment Day 8 in each period) will have duration of approximately 5 hours where safety and tolerability assessments as well as spirometry measurements will be performed pre-dose and up to 4 hours post-dose.

Study treatment administration during all the visits at the sites (Day 1, Day 2, Day 8, and Day 14 of each treatment period) will be supervised by study personnel.

At Visits 3 to 11, a subset of 36 patients will undergo PK assessments. Blood samples will be collected pre-dose and up to 24 hours post-dose.

On Day 1 of treatment periods 2 and 3, a FEV₁ stability test will be performed pre-dose. FEV₁ stability check will be based on the pre-best test review (BTR). At Visits 6 and 9 the mean of the pre-dose FEV₁ (mean of the 2 measured values) should be within (±)20% or (±)200 mL compared to the pre-dose FEV₁ (mean of the 2 measured values) of the first treatment period (Visit 3).

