9.4 Statistical analyses

Analyses will be performed by PAREXEL except the derivation of the PK parameters, which will be performed by Covance. A comprehensive statistical analysis plan (SAP) will be developed and finalised before database lock and will describe the patient populations to be included in the analyses, and procedures for accounting for missing, unused, and spurious data. This section is a summary of the planned statistical analyses of the primary and secondary endpoints. Any deviations from this plan will be reported in the CSR.

All results will be presented by treatment with descriptive statistics appropriate to the nature of the variables. Demographic and baseline characteristics will be presented. For continuous variables, the number of non-missing observations, mean, SD, standard error (SE) of the mean, 95% confidence interval (CI) of the mean (except safety data), median, first and third quartiles, minimum and maximum will be presented. For categorical variables: counts (n) and percentages (%) [where specified] will be presented. These summaries will be provided by time point of assessment as appropriate.

The SAS[®] version 9.3 or later will be used for the data analysis. A complete set of raw data listings will be appended to the final CSR. All tables, figures and listings will be presented in Word and Portable Document Format documents without any manual editing, (ie, they will appear unmodified as programmed by means of the statistical package).

In general, there will be no imputation of missing data for the safety or efficacy analyses. Additional details will be provided in the SAP.

All personnel involved with the analysis of the study will remain blinded until database lock and Clinical Study Protocol deviations identified.

Deviations from the protocol will be assessed as “important” or “not-important”. Important deviations from the protocol may lead to the exclusion of patients from the PP population and/or other populations. Deviations will be defined before database hard lock and unblinding. Important deviations will include the following:

- Violation of inclusion and/or exclusion criteria.
- Administration of prohibited concomitant medications that are expected to influence the measurement of the primary endpoint.

All important protocol deviations will be listed by patient for all randomised patients. Further details will be described in the SAP.

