42	Participation in another clinical study with investigational drug or device within the last 30 days or 5 half-lives (whichever is longer) prior to Screening.	Yes ⁺⁺⁺	No	Yes ⁺⁺⁺	No
43	Patient with known human immunodeficiency virus (HIV) infection or chronic hepatitis B or C infection.	Yes	No	No	No
44	Patient did not fulfill fasting requirements on Day 1, 8, and 14 before IP administration and following dose administration.	Yes ⁺⁺	No	No	No
45	Salbutamol not withheld at least 6 hours prior to any spirometry test for the study.	Yes	No	No	No
46	Ipratropium not withheld at least 8 hours before visits 3, 6, and 9 and during all treatment periods.	Yes	No	No	No
47	Patient could not abstain from list in protocol section 5.3	Yes	No	No	No
48	Patient who had 2 or more exacerbations of COPD within the last year prior to Screening	Yes	No	No	No
49	Patient unable to abstain from protocol-defined prohibited medications during the study, in the opinion of the investigator.	Yes ⁺⁺	No	Yes ⁺⁺	No
50	Patient is screening failure, but received study drug.	Yes	Yes	Yes	Yes
51	Incorrect study medication received.	Yes ⁺⁺	No	Yes ⁺⁺	No

Item #	Event description	Excluded from analysis set			
		P-PS	SS	PKS	FAS
52	Incorrect dose of study medication received.	Yes ⁺⁺	No	Yes ⁺⁺	No
53	Patient did not take any IP	Yes ⁺⁺	Yes	Yes ⁺⁺	Yes ⁺⁺
54	IP not taken at the study site at 9:00 AM±2 hours on Day 1 (Visits 3, 6 and 9).	Yes ⁺⁺	No	Yes ⁺⁺⁺	No
55	IP not taken within ±1 hours of dosing time of Day 1 and between 7 AM and 11AM on subsequent days of each treatment period.	Yes ⁺⁺	No	Yes ⁺⁺⁺	No
56	Patient has taken any of the restricted medications on a different regimen than the described in the protocol (Table 5, section 6.5).	Yes ⁺⁺	No	Yes ⁺⁺⁺	No
57	Procedure not performed (missing PK samples to prevent calculation of PK parameters).	No	No	Yes ⁺⁺	No
58	Study assessments (For example cough monitoring, spirometry, CC1 i-Stat, 12 Lead ECG and/or vital signs) are not performed at the scheduled timepoints.	No	No	No	No
59	Missing baseline data for the spirometry (FEV1 main variable)	Yes ⁺⁺	No	No	No
60	FEV1 and FVC measurements performed outside tolerance window	No	No	No	No
61	Fulfilling withdrawal criteria during the study but not withdrawn.	Yes	No	No	No
62	Fatal or life-threatening AE was not reported to the appropriate AstraZeneca representatives within 1 calendar day of initial receipt.	No	No	No	No

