3.3 Efficacy variables

3.3.1 Pulmonary function variables

Pulmonary function will be assessed using spirometry performed as follows:

- Pre-dose spirometry is performed before the morning daily dose at Day 1, Day 8, and Day 14 of each treatment period. Two sets of measurements will be performed during

the hour preceding the scheduled morning study drug administration, allowing approximately 45 min between them.

- Trough FEV₁ values are defined as the mean of the values obtained at 23 hours and 23 hours 45 minutes after the morning IP administration on Day 1 and Day 14 (i.e. obtained on Day 2 and Day 15). On Day 8, TFEV₁ value is defined as the mean of the FEV₁ pre-dose values (-1 hour and -15 min).

If one of the two measurements is missing, the non-missing measurement will be used as the trough value.

- Definition above also applies to FVC measurements.
- 4 hour serial spirometry is performed at Day 8 of each treatment period; spirometry will be performed post-dose at 15 minutes, 30 minutes, 1 hour, 2 hours, and 4 hours.
- 8 hour and 24 hour serial spirometry is performed at Day 1 and 14 of each treatment period; spirometry will be performed post-dose at 15 minutes, 30 minutes, 1 hour, 2 hours, 4 hours, 8 hours, 12 hours, 23 hours and 23:45 hours.
- The FEV₁ peak value at a visit is defined as the highest value observed during the 4 hour period immediately following the morning study drug administration at that visit (ie, the maximum value observed at 15 minutes, 30 minutes, 1 hour, 2 hours or 4 hours post-dose).

AUC is defined as the area under the curve.

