For t= 4, 8, 12 and 24 AUC is calculated from zero time to t hours (AUC_{0-t}), using the trapezoidal method, divided by the corresponding duration (ie, 4, 8 and 24 hours, respectively) to give the AUC_{0-t/th} values (where t is either 4, 8 or 24) in litres. Non-missing FEV₁, at the following time points are required in order to calculate the normalised AUC_{0-4/4h}: pre-dose; at least one value between 0 and 2 hours and the value at 4 hours post-dose. Similarly, nonmissing- FEV₁ values at the following time points are required in order to calculate the normalised AUC_{0-8/8h}: predose-; at least one value between 0 and 4 hours and the value at 8 hours post-dose. For AUC_{0-24/24h}, nonmissing- FEV₁ values at the following time points are required in order to calculate the normalised AUC_{0-24/24h}: predose-; at least one value between 0 and 8 hours and at least one value post 8 hours post-dose; otherwise the normalised AUC_{0-t/th} will be missing.

Notice that in case that the 23:45 timepoint is missing and only the 23h timepoint is used, the AUC₀₋₂₄ will still be normalized by 24 and AUC_{0-24/24h} computed. The raw AUC will be used (rather than the logs), since the distribution of the FEV₁ data is expected to approximate to a normal distribution.

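### The rule for AUC0-24/24h accepts an FEV1 profile that stops at 12 h and still divides its area by 24

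*SAP*

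**What the plan says.** SAP 3.3.1 finds each FEV1 AUC from time zero by the trapezoidal method, "divided by the corresponding duration (ie, 4, 8 and 24 hours, respectively". For the 24 h window it needs a pre-dose value and "at least one value between 0 and 8 hours and at least one value post 8 hours post-dose"; if these are not available the result is missing.

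On Days 1 and 14 the planned post-dose tests end with "4 hours, 8 hours, 12 hours, 23 hours and 23:45 hours". The tests later than 8 h are therefore at 12, 23 and 23:45 h.

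The shorter windows have a stricter rule. With the pre-dose value, the 8 h AUC needs "at least one value between 0 and 4 hours and the value at 8 hours post-dose", and the 4 h AUC likewise needs its 4 h value. AUC0-12/12h has no completeness rule.

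The SAP discusses one shortened 24 h profile: "Notice that in case that the 23:45 timepoint is missing and only the 23h timepoint is used". In that case the divisor stays at 24. On missing data, Protocol 9.4 says: "In general, there will be no imputation of missing data for the safety or efficacy analyses".

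AUC0-24/24h on Days 1 and 14 is a listed secondary endpoint (SAP 1.1.1). It is analysed on the full analysis set under SAP 4.2.4.

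**The concern.** A single 12 h value satisfies the late-value condition, so a patient with no test after 12 h still gets an AUC0-24/24h. Nothing supplies area between 12 and 24 h, yet the divisor remains 24. Arithmetically this treats the change from baseline as zero for the second half of the day.

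The value is not set to missing; it enters the mixed model pulled towards zero. SAP 4.1.1 gives estimation as the main purpose of the study, so a rule that distorts an estimate matters even without a formal test. If such profiles are equally common on all treatments, a true difference is diluted. If they are more common on one treatment, the difference is biased, and the direction depends on which treatment it is.

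**Working it through.** The plan gives no figure to reproduce here, so the check applies its rule to assumed profiles.

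**Inputs from the documents**
- Test times in hours: 0 (pre-dose), 0.25, 0.5, 1, 2, 4, 8, 12, 23, 23.75 (SAP 3.3.1).
- Divisor 24; no extrapolation.
- Yardstick for size: SD of differences 220 mL and 54 patients, for trough FEV1 (Protocol 9.2).

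**Assumptions**
- Day 1 change from baseline, zero at pre-dose. The response from the first post-dose test onward is either flat at 200 mL or on a straight line over 24 h from 300 to 100 mL, or from 300 to 0 mL. The documents give no 12 to 24 h data for this trial.
- The share of profiles that stop at 12 h. The documents give none.

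**Step 1: one profile.** Value = (trapezoidal area up to the last test) / 24. For the flat 200 mL profile:
- area to 12 h = 0.25 × 100 + 11.75 × 200 = 2375 mL·h, and 2375 / 24 = 99.0 mL;
- area carried to 24 h = 0.25 × 100 + 23.75 × 200 = 4775 mL·h, and 4775 / 24 = 199.0 mL.

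All three shapes, in mL, with the change from the 24 h reference:

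| Shape | Carried to 24 h | Last test 23:45 | Last test 23 h | Last test 12 h |
|---|---|---|---|---|
| Flat 200 | 199.0 | 196.9 (−1.0%) | 190.6 (−4.2%) | 99.0 (−50.3%) |
| 300 to 100 | 198.4 | 197.4 (−0.5%) | 194.1 (−2.2%) | 123.4 (−37.8%) |
| 300 to 0 | 148.4 | 148.4 (0.0%) | 148.2 (−0.2%) | 110.9 (−25.3%) |

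The loss from stopping at 12 h is 100, 75 and 37.5 mL. Stopping at 23 h costs little.

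**Step 2: other shapes.** A second set of profiles rises to a peak at 2 h and then declines; here the reference is the same profile ending at 23:45. The loss is about 25% to 52%. Protocol 2.3 gives peak effects of 427 to 694 mL and trough effects of 267 to 414 mL after single doses in asthma patients, a trough-to-peak ratio of about 0.60 to 0.63. Profiles with those values lose 43.7% to 45.7%.

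**Step 3: treatment difference.** A flat response loses half its value, so 200 mL loses 100 and 100 mL loses 50. With shares pA and pB of profiles stopping at 12 h, the shift in a true 100 mL difference is −(pA × 100 − pB × 50) mL:

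| pA (200 mL) | pB (100 mL) | Shift |
|---|---|---|
| 2% | 2% | −1.0 mL |
| 5% | 5% | −2.5 mL |
| 10% | 10% | −5.0 mL |
| 5% | 0% | −5.0 mL |
| 0% | 5% | +2.5 mL |

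Two treatments that both truly give 200 mL would appear to differ by 0.05 × 100 = 5.0 mL if 5% of profiles on only one of them stopped at 12 h.

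**Step 4: yardstick.** 220 / √54 = 29.9 mL. Shifts of 1.0 to 5.0 mL are 3.3% to 16.7% of that standard error.

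**The case against.** The strongest reply is that the case should be rare. Protocol 1.2 says the Day 1 and Day 14 visits "will include an overnight stay in the unit". Other assessments are due at 24 h, and the two late tests define trough FEV1, including the primary endpoint, so sites have every reason to obtain them. Both must be missed while the 12 h test is present. On that view shares of 5% or 10% are high. This stands, and it is why the expected effect is small.

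It can also be said that the SAP never states what happens to a 12 h profile. That is true, but the result follows from the acceptance rule, the general divisor and the absence of any extrapolation. The note on a missing 23:45 value does not make the 23 h value a requirement.

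Three further limits are fair:
- A negative change, plausible on placebo, moves up towards zero; it does not fall.
- SAP 3.3.1.3 words only the 4 h AUC as a change from baseline. If absolute FEV1 were averaged over 24 h and baseline then subtracted, the error would be much larger: with an assumed 1.5 L baseline and a flat 200 mL response, (0.25 × 1.6 + 11.75 × 1.7) / 24 − 1.5 = −0.65 L.
- SAP Table 1 item 58, under which assessments that "are not performed at the scheduled timepoints" exclude nobody, offers no protection. But analysis-set membership would not settle whether a derived value is missing in any case.

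**Conclusion.** The concern holds. As written, the rule turns a 12 h profile into a 24 h average that is too close to zero: about 25% to 50% too low for one patient with a positive response, given the assumed shapes. The effect on a treatment difference is probably a few mL at most. It rests on assumed shares, because the documents do not say how often both late tests are missed. The problem is confined to AUC0-24/24h on Days 1 and 14; trough FEV1 on Day 15 is not affected. Keeping 24 as the divisor when the 23 h value is present is sound.

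The missing completeness rule for AUC0-12/12h is a lesser, separate gap. The absence of 12 from the list of divisors is only untidy, since the same sentence names 12 among the windows.

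**What to change.** In SAP 3.3.1, require for AUC0-24/24h the pre-dose value, at least one value from 0 to 8 h, and the 23 h or 23:45 value; otherwise set it to missing. In the same edit, require the 12 h value for AUC0-12/12h and add 12 to the divisors. This matches the SAP's existing 4 h and 8 h rules.

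Keep 24 as the divisor for profiles ending at 23 h or 23:45. Dividing a 23 h profile by 23 would overstate declining responses: 4658.3 / 23 = 202.5 against 198.4 mL (+2.1%) for 300 to 100 mL, and 3556.25 / 23 = 154.6 against 148.4 mL (+4.2%) for 300 to 0 mL. Dividing a 12 h area by 12 is no remedy either. It doubles the last column of the first table, giving 246.9 against 198.4 mL and 221.9 against 148.4 mL for the two declining shapes.

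The cost is one changed and one added sentence, plus a small change to the derivation program before database lock. No new data are needed. A few incomplete profiles become missing and are left to the planned mixed model.

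The edit does not deal with sparse early data. A flat 200 mL profile with only pre-dose, 8 h and 23:45 values would still pass and give (800 + 3150) / 24 = 165 mL against 199 mL.

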3.3.1.1 Primary outcome variable

The primary variable to assess the primary objective is the change from baseline (pre-dose) in Trough FEV₁ at Day 15 (ie, after 14 days of treatment).

3.3.1.2 Secondary FEV₁ -related variables

Secondary efficacy variables that will be assessed are the following:

- Change from baseline in Trough FEV₁ on Day 2, and Day 8
- Change from baseline in Peak FEV₁ on Day 1, Day 8, and Day 14
- Change from baseline in Trough FEV₁ over treatment duration (Day 1 to Day 15)
- Change from baseline in Peak FEV₁ over treatment duration (Day 1 to Day 14)

3.3.1.3 Other FEV₁ -related variables

- Change from baseline in FEV₁ AUC_(0-4/4h) (area under the curve for the change in FEV₁ from baseline to 4h, normalised by the time window) on Day 1, Day 8, and Day 14
- FEV₁ AUC_(0-8/8h) on Day 1, and Day 14
- FEV₁ AUC_(0-12/12h) on Day 1, and Day 14
- FEV₁ AUC_(0-24/24h) on Day 1, and Day 14

3.3.2 Other efficacy variables

3.3.2.1 Total Breathlessness, Cough Sputum Scale (BCSS) score questionnaire and cough, breathlessness and sputum individual domain scores

The daily change from baseline obtained after treatment in Total BCSS score and cough, breathlessness and sputum individual domain scores will be averaged

- over Day 1 to Day 8 to construct the Day 8 endpoints
- over Day 9 to Day 14 to construct the Day 14 endpoints
- over Day 1 to Day 14 to construct the Day 14 endpoints for the analysis of the whole treatment

3.3.2.2 COPDCompEx, Cough VAS and Cough Monitoring

A composite endpoint for exacerbations (moderate or severe) in COPD (COPDCompEx) will be derived and analysed. COPDCompEx combines exacerbations with events defined from patient daily diaries. The definitions for the different types of events are as follows:

- Exacerbations: episodes leading to one or more of the following; hospitalisation, emergency room visit, treatment with oral corticosteroids, or treatment with antibiotics.
- Diary events: defined by threshold and slope criteria using the following diary variables: individual domains of the breathlessness, cough, and sputum scale and rescue medication use.
- Dropouts: Dropouts due to lack of efficacy (if possible to judge) occurring during treatment periods.

The following COPD and cough variables will be assessed:

- Change from baseline in cough VAS on Day 8 and Day 15
- Change from baseline in number of coughs as measured by cough monitoring on Day 14
- Time to first COPDCompEx.

3.3.2.3 COPD Assessment Test (CAT)

Change from baseline in CAT from Day 1 to Day 8, from Day 9 to Day 14 and during the whole treatment duration will be described.

3.3.2.4 Rescue medication use (Salbutamol)

The daily change from baseline obtained after treatment in rescue medication will be averaged

- over Day 1 to Day 8 to construct the Day 8 endpoint
- over Day 9 to Day 14 to construct the Day 14 endpoint

3.4 Pharmacokinetic variables

The PK analyses of the plasma concentration data for AZD8871 and its primary metabolite LAS191861 will be performed by the Covance Clinical Pharmacology Alliance (CPKA) on behalf of AstraZeneca.

The actual sampling times will be used in the plasma PK parameter calculations.

PK parameters will be derived using non-compartmental methods with Phoenix[®] WinNonlin[®] Version 6.4. or higher. PK analyses will be conducted according to AstraZeneca SOPs for PK analyses, if not otherwise indicated.

Plasma concentrations below the lower limit of quantification (BLQ) from the time of pre-dose sampling ($t=0$) up to the time of the first quantifiable concentration will be set to a value of 0. After this point, BLQ plasma concentrations will be set to missing for all concentration profiles. If 2 or more consecutive BLQ concentrations are followed by quantifiable concentrations in the terminal portion of the concentration-curve, the profile will be deemed to have terminated and therefore these quantifiable values will be set to missing for the calculation of the PK parameters unless there is a scientific rationale not to do so; this will be documented in the PK analysis notes. If an entire concentration-time profile is BLQ, the profile is excluded from the PK analysis.

Area under the plasma concentration-curve will be calculated using trapezoidal methods when concentrations are increasing and logarithmic trapezoidal method when concentrations are decreasing.

Three concentrations higher than the lower limit of quantification (LLOQ) are required as a minimum for an AUC parameter to be determined, with at least one of these concentrations following C_{max} .

When possible, the following PK parameters will be determined for AZD8871 and its primary metabolite, LAS191861 from plasma concentration-time data:

Day 1:

C_{max} - Maximum observed plasma concentration, taken directly from the individual concentration-time curve

t_{max} - Time to reach maximum observed plasma concentration, taken directly from the individual concentration-time curve

AUC_{last} - Area under the plasma concentration-curve from time zero to the time of last quantifiable concentration

t_{last} - Time to reach last quantifiable concentration

$AUC_{(0-24)}$ - Area under the plasma concentration-curve from time zero to 24 hours post-dose

For metabolite LAS191861 only:

MRC_{max} - Metabolite to parent ratio for C_{max}

$MRAUC_{(0-24)}$ - Metabolite to parent ratio for $AUC_{(0-24)}$

$MRAUC_{last}$ - Metabolite to parent ratio for AUC_{last}

Day 14:

C_{max} - Maximum observed plasma concentration, taken directly from the individual concentration-time curve

t_{max} - Time to reach maximum observed plasma concentration, taken directly from the individual concentration-time curve

AUC_{last} - Area under the plasma concentration-curve from time zero to the time of last quantifiable concentration

t_{last} - Time to reach last quantifiable concentration

$AUC_{(0-24)}$ - Area under the plasma concentration-curve from time zero to 24 hours post-dose

C_{avg} - Average plasma concentration during a dosing interval, estimated as $AUC_{(0-24)}/24$

%Fluc - Fluctuation index during a dosing interval estimated as $100 * (C_{max} - C_{min}) / C_{avg}$ (%), where C_{min} is the minimum concentration at the end of the dosing interval

Rac (C_{max}) - Accumulation ratio for C_{max} estimated as (C_{max} on Day 14 / C_{max} on Day 1)

Rac (AUC_{0-24}) - Accumulation ratio for AUC_{0-24} estimated as ($AUC_{(0-24)}$ on Day 14 / $AUC_{(0-24)}$ on Day 1)

For metabolite LAS191861 only:

MRC_{max} - Metabolite to parent ratio for C_{max}

$MRAUC_{(0-24)}$ - Metabolite to parent ratio for $AUC_{(0-24)}$

$MRAUC_{last}$ - Metabolite to parent ratio for AUC_{last}

